3.0 RESEARCH DESIGN AND METHODS

3.1 Drug/Device Information: NOT APPLICABLE

3.2 Type of Study: (Table 3: Individual Timeline): This is a longitudinal, efficacy randomized controlled trial (RCT). Veterans with MDD will be evaluated for eligibility and randomized to a 12-week intervention of a twice-weekly yoga and coherent breathing or walking group. As there is evidence that exercise improves mood in unipolar depression, the walking group will serve as an active control condition.(47) The policy for Common Data Elements will be incorporated into the data collection matrix. The Consolidated Standard of Reporting Trials (CONSORT) will be used to ensure the quality of reporting for this RCT.(48) The **primary dependent variable** will be changes in the Hamilton Depression Rating Scale (covering a 2 week period), and mood and anxiety scales (designed for repeated use, such that changes from pre to post intervention can be gauged), measured using valid and reliable psychological instruments obtained at screening, intervention weeks 4, 8, and 12, and before each MRS scan. The **secondary dependent variable** will be brain gamma amino-butyric acid (GABA) levels measured by magnetic resonance spectroscopy (MRS) in the left thalamus, the same region used in our prior studies.(9, 53, 65) The thalamus has the technical advantage of providing high quality spectra, has a high concentration of GABAergic neurons, and thus a high GABA signal, in which changes can be detected. The thalamus is also anatomically connected to other regions of interest. GABA levels will be measured by MRS in 3 separate scan acquisitions: before randomization (Scan 1), after 12-weeks of the yoga or walking intervention (Scan 2), followed immediately by the group assigned intervention and the final scan (Scan 3). The **third dependent variable** will be respiratory sinus arrhythmia (RSA) a component of heart rate variability (HRV) that is an accurate index of vagal influences on the heart.RSA will be measured before each scan and before and after an intervention at week 4, week 8 and week 12. Medications also are evaluated at weeks 4, 8, and 12. Two and six month follow-up phone calls will assess depression, quantity of yoga practice, and barriers to practice.

3.3.1. Sub-Study Participation: This is not a multisite study. There will be a contract with the McLean Hospital for goods and services regarding the imaging component of this study.

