Potential participants are excluded for a history of psychosis, bipolar illness, and suicidal ideation with intent or a suicide attempt within the last year. Axis-I disorders that would interfere with study participation are exclusionary such as Obsessive Compulsive Disorder or Agoraphobia that would prevent attendance at the intervention. Alcohol Use Disorders with more than 3 DSM-IV criteria. Substance Use Disorders in Remission are allowed. Because inversion can increase intraocular pressure, individuals with a retinal hemorrhage or glaucoma cannot participate unless they receive clearance from their ophthalmologist. Neurologic conditions, which would effect scan results, are exclusionary such as stroke, seizures, brain surgery, HIV and other CNS disorders. The ability to participate in both interventions is required, such that a person who walks with a cane would not be enrolled as it would be a concern that they would either not be able to walk at 2.5 miles an hour for one hour or that if they did it could potentially harm them. Individuals with a history of spine surgery could be excluded depending on the surgery. Individual with cardiovascular or respiratory disease would require careful evaluation that could include a discussion with their physician. Traumatic Brain Injury with greater than 30 minutes loss of consciousness would be exclusionary. During the screening process, the potential participants have to complete a 3-minute step test (See Step Protocol). If the participant is unable to perform the step test, they would be excluded from the study. If during the physical exam, the PI is concerned about the potential participants ability to participate, they maybe asked to attempt to touch their toes, and to get down and then up from a yoga mat or to walk the circuit that they would walk during the walking intervention.

3.3.2.5. Inclusion Criteria:

- (1) male and female Veterans ages 18 to 65;
- (2) Fluent in English;
- (3) Understands the risks and benefits of the study as listed in the Post Consent Quiz
- (4) Females must agree to use an acceptable form of birth control [see 4.6.1.15 for acceptable contraception] and do not intend to become pregnant during the study
- (5) Females have a negative pregnancy test or a serum progesterone in the non luteal stage defined by less than or equal to 1.3 ng/ml prior to Scan 1.
- (6) Meets criteria for MDD on the SCID-5
- (7) Hamilton Rating Scale for Depression (HDRS) scores \geq to 14 at screening

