- (8) If subjects have been taking antidepressants that target a monoamine system, the dose has been stable for at least one month with no anticipated changes during the study; or no antidepressants for one month
- (9) If subjects have been in a stable form of psychotherapy for three months, with no anticipated changes in their psychotherapy during the study (this would exclude time-limited manual-driven therapies such Cognitive Behavioral Therapy); or no psychotherapy for three months
- (10) Reliable contact information provided
- (11) Subject weighs up to 300 lbs. at the discretion of the PI.

(12) Subject has completed all required screening instruments and evaluations

3.3.2.6. Exclusion Criteria:

- (13) History of psychosis (substance-induced psychotic disorder and psychotic disorder due to another medical condition are allowable if fully resolved)
- (14) History of bipolar illness
- (15) History of suicidal ideation with intent in the last year according to the Columbia Suicide Safety Rating Scale (C-SSRS)
- (16) Subject has a history of suicidal attempt with intent to injure in the last year according to the C-SSRS.
- (17) Desire to be treated for MDD with a new treatment during the study such as pharmacotherapy somatic therapy or psychotherapy.
- (18) A contraindication to magnetic resonance evaluation (e.g., pregnancy, a cardiac pacemaker, ferrous implant including shrapnel, or intrauterine devices (IUDs) with copper, claustrophobia that would prevent scanning, some tattoos with black ink on the head including permanent eyeliner).
- (19) Current mind-body practice (e.g., yoga, Tai Chi, Qigong, breathing practices, or meditation) defined as more than 6 one-hour sessions in the last 6 months.
- (20) The use of intra-uterine devices with progesterone that interferes with the ability to determine the non-luteal phase required to schedule Imaging Session 1.
- (21) Participates in physical exercise > 5 hours/week that is equivalent to or greater than 6 metabolic equivalents (METs) in intensity.
- (22) Has been treated psychotropic medications such as mood stabilizers (e.g., Valproic Acid, Carbamazepine, or Lithium) in the last three months.

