3.3.2.8. Group Assignment, & Blinding: All investigators are blind to group assignment prior to randomization. Blinding will be guided by the Cochrane Collaboration Tool for assessing risk of bias in randomized trials.(14) The study physicist, [name], and [name], the RSA expert, will be blind to group assignment. Investigators who administer subjective instruments (i.e., Hamilton Rating Scale for Depression and CAPS) will be blind to group assignment. Subjects will fill out self-reporting mood and psychological scales in paper form that will be entered into the VA network by research staff. All VA paper documents with sensitive information will be secured in a locked filing cabinet in a designed VA Office. ECG data used for RSA analysis and MRS data will be labeled with a blinding code provided by the Data Coordinating Center, such that ECG data and MRS data are stripped of identifying information, including removal of study ID, date of acquisition and timing of the assessment (baseline, pre or post the intervention at weeks 4, 8, or 12) before being sent [name] for analysis. As subjects are not blind to the intervention, there is no procedure to break the blind for clinical reasons.

3.3.2.9. Gender Differences: While we will equally recruit both genders, due to the demographics of the VABHCS population, it is anticipated that more males will be recruited, which will provide much needed information on the efficacy of this intervention in men. Due to the influence of menstrual cycle phase and associated changes of progesterone on brain GABA/Cr levels, serum levels of progesterone will be drawn before each scan, with progesterone levels less than or equal to 1.3 ng/ml being considered the non-luteal stage, a stage when GABA/Cr is not influenced by menstrual cycle.(75) Serum progesterone levels will be drawn at the VABHCS.

3.3.2.10. Subject Compliance and Payment: Compliance with group session attendance and homework is important, both as an assessment of treatment acceptance and as a measure of the "dose" of the intervention required for symptom reduction. Attendance at the interventions will be recorded on an attendance sheet; home practice of yoga and walking will be recorded on the weekly PAR. Subjects will be paid for their time: \$10 for each group session, \$20 for the week 4 evaluations, \$40 for the week 8 evaluations, \$60 for the week 12 evaluations, and \$40 for each MRS scan for a maximum of \$480.

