3.3.2.13. Clinically Significant Abnormalities: If a participant's tests have clinically significant

abnormalities or unexpected findings, they will be told. Specifically, females will be told if they are pregnant. If the serum progesterone level is not less than or equal to 0.03 ng/ml, the participant will be told and possibly asked to repeat the test. If there is a clinically significant finding on the anatomic MRI, the participant will be informed by the study PI, an M.D., within 7 days of receipt of the report by phone or in person. It is McLean's policy to call the listed physician if there is an abnormality found during the MRI reading that requires immediate attention. If the participant gives written permission a copy of the report will be forwarded to the identified physician.

3.3.2.14. Assessment for Suicidality and Safety Plan: Participants are screened weekly for suicidality by use of an Adverse Events sheet that they are required to turn in at the first session of the week, either in-person or virtual. This form may be collected by the Project Manager, or research staff. Due to the addition of virtual interventions, the form can be filed out by research staff over the phone. If there is an indication of increased depression or suicidal ideation, the project manager will inform the research staff or the PI that an assessment of the participant is required. There are also in-person evaluations by research staff at weeks 4, 8, and 12 where participants are assessed for suicidality and increased depressive symptoms. This study excludes individuals with a history of suicidal ideation with intent or a suicide attempt in the last year. This study allows suicidality without intent, which is some individuals is present for years.

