4.4 Inclusion/Exclusion Criteria

4.4.1. Inclusion Criteria:

- 1 male and female Veterans ages 18 to 65;
- 2 Fluent in English;
- 3 Understands the risks and benefits of the study as listed in the Post Consent Quiz
- 4 Females must agree to use an acceptable form of birth control [see Human Subjects] and do not intend to become pregnant during the study
- 5 Females have a negative pregnancy test or a serum progesterone in the non luteal stage defined by less than or equal to 1.3 ng/ml prior to Scan 1.
- 6 Meets criteria for MDD on the SCID-5
- 7 Hamilton Rating Scale for Depression (HDRS) scores \geq 14 at screening
- 8 If subjects have been taking antidepressants that target a monoamine system, the dose has been stable for at least one month with no anticipated changes during the study; or no antidepressants for one month
- 9 If subjects have been in a stable form of psychotherapy for one month, with no anticipated changes in their psychotherapy during the study (this would exclude time-limited manual-driven therapies such Cognitive Behavioral Therapy); or no psychotherapy for 1 month
- 10 Reliable contact information provided
- 11 Subject weighs up to 300 lbs. at the discretion of the PI.
- 12 Subject has completed all required screening instruments and evaluations

Exclusion Criteria:

- 13 History of psychosis (substance-induced psychotic disorder and psychotic disorder due to another medical condition are allowable if fully resolved)
- 14 History of bipolar illness
- 15 History of suicidal ideation with intent in the last year according to the Columbia Suicide Safety Rating Scale (C-SSRS)
- 16 Subject has a history of suicidal attempt with intent to injure in the last year according to the C- SSRS.
- 17 Desire to be treated for MDD with a new treatment during the study such as pharmacotherapy somatic therapy or psychotherapy.
- 18 A contraindication to magnetic resonance evaluation (e.g., pregnancy, a cardiac pacemaker, ferrous implant including shrapnel, or intrauterine devices (IUDs) with copper, claustrophobia that would prevent scanning, some tattoos with black ink on the head including permanent eyeliner).
- 19 Current mind-body practice (e.g., yoga, Tai Chi, Qigong, breathing practices, or meditation) defined as more than 3 one-hour sessions in the last 3 months.
- 20 The use of intra-uterine devices with progesterone that interferes with the ability to determine the non-luteal phase required to schedule Imaging Session 1

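### The progesterone level that triggers notification and a possible retest (0.03 ng/ml, Protocol 3.3.2.13) does not match the protocol's non-luteal cut-off of 1.3 ng/ml

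*Protocol*

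**What the plan says.** Protocol 3.3.2.13 describes what participants are told when a test is abnormal or unexpected. Pregnancy has its own sentence. The progesterone sentence follows. Its condition is "If the serum progesterone level is not less than or equal to 0.03 ng/ml". Its consequence is that "the participant will be told and possibly asked to repeat the test". Telling her is mandatory and the repeat is discretionary.

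Three other places put a number on progesterone, and all give 1.3 ng/ml:

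- Inclusion criterion 5 in 4.4.1 accepts, as an alternative to a negative pregnancy test, a "serum progesterone in the non luteal stage defined by less than or equal to 1.3 ng/ml prior to Scan 1".
- Inclusion criterion 5 in 3.3.2.5 has the same alternative, "defined by less than or equal to 1.3 ng/ml prior to Scan 1".
- Section 3.3.2.9 (Gender Differences) explains that menstrual phase affects brain GABA/Cr and that "serum levels of progesterone will be drawn before each scan". The same sentence sets the limit: "with progesterone levels less than or equal to 1.3 ng/ml being considered the non-luteal stage".

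Exclusion criterion 20, in both lists, refers to "the non-luteal phase required to schedule Imaging Session 1" without giving a number. The SAP does not mention progesterone.

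**The concern.** The protocol measures progesterone for one stated reason: to establish that a woman is in the non-luteal stage, so that menstrual phase does not disturb the GABA measurement. A rule for when to tell her about the result and consider repeating the test would be expected to use the same cut-off. It uses a much lower one, stated once and without a rationale.

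Staff who follow 3.3.2.13 as written would have to report a result to a woman whom 3.3.2.9 calls non-luteal, under a heading that presents it as clinically significant. They could also ask her for another blood sample that serves no stated purpose. What is at stake is participant communication and an avoidable venipuncture, not the validity of the GABA comparison.

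**Working it through.** No sample-size or error-rate figure is involved. The check sets the thresholds side by side; all are for serum progesterone in ng/ml.

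| Place in Protocol | Role | Level |
|---|---|---|
| 3.3.2.5, inclusion criterion 5 | eligibility, before Scan 1 | ≤ 1.3 |
| 4.4.1, inclusion criterion 5 | eligibility, before Scan 1 | ≤ 1.3 |
| 3.3.2.9 | non-luteal stage, draw before each scan | ≤ 1.3 |
| 3.3.2.13 | tell participant, possibly retest | > 0.03 |

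**Size of the mismatch.** 1.3 / 0.03 = 43.3, so the trigger is about 43 times lower than the cut-off.

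**What happens at each level.**

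- At or below 0.03: non-luteal, no notification. The rules agree.
- Above 0.03 and up to 1.3: non-luteal under 3.3.2.9, but notification is required and a retest possible under 3.3.2.13. The rules conflict here.
- Above 1.3: not non-luteal. Because 1.3 exceeds 0.03, notification is also triggered. The rules agree, and no luteal-phase woman escapes the trigger.

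The error therefore runs in one direction: too many notifications, never too few.

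**Could 0.03 have its own purpose?** It is not described as an assay limit, and it is not needed as a pregnancy flag because pregnancy has a separate sentence. Its wording also follows the form of the 1.3 rules. Nothing in the documents supports a distinct use.

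**How often per woman.** Section 3.2 states: "GABA levels will be measured by MRS in 3 separate scan acquisitions: before randomization (Scan 1"), with Scan 2 after the 12 weeks and Scan 3 straight after a further intervention session. One draw before each scan, read literally, gives 3 draws for a woman with all three scans; one per imaging session gives 2. Section 3.3.2.9 has the blood drawn at the VA site while scanning is at McLean, which makes 2 the more workable reading.

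**How many women.** This cannot be derived: the documents do not say how many women fall between 0.03 and 1.3 ng/ml, how many are drawn before Scan 1, or how often a retest would be requested. For scale only, using the 10% female estimate in 4.2:

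- Randomised: 0.10 × 84 = 8.4 (total from 3.5.2) to 0.10 × 100 = 10 (total from 3.3.2.2 and 4.5.2.9).
- Screening interviews: 0.10 × 173 = 17.3 (total from 3.3.2.2 and 4.5.2.9). Scan 1 precedes randomisation, so first draws come from this larger group, though not everyone interviewed reaches Scan 1.

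None of these is a ceiling. Section 4.1 expects that the female share may exceed that of the hospital's population.

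**The case against.** The strongest reply is that these are not two values for one rule. The 1.3 ng/ml figure defines the non-luteal stage; the sentence in 3.3.2.13 only governs what a participant is told, and mentions neither luteal phase, eligibility nor scheduling. A site could obey every sentence at once by telling a woman her value and still scanning her at 1.3 or below. That is true, and it is why the protocol remains workable. It does not explain why a result the protocol accepts should be reported under the abnormalities heading.

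Four narrower points also have some force:

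- Criterion 5 is an either/or. Read literally, a negative pregnancy test satisfies it at any progesterone level, so the eligibility role of 1.3 is looser than it first appears. The mismatch survives, because 3.3.2.9 gives 1.3 as the non-luteal limit in the same sentence that calls for a draw before each scan.
- The progesterone sentence does not itself call the result abnormal or unexpected. That label comes from the opening of 3.3.2.13. It is the natural reading, but it is a reading.
- The phase requirement in the criteria is tied to Scan 1, and nothing says that a later scan is postponed on the result. A retest at the second imaging session is therefore less likely, although the duty to tell the woman still applies.
- That 1.3 is the intended figure is an inference. The documents establish the mismatch, not the correction.

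**Conclusion.** The concern holds, at minor severity. The mismatch is certain: 0.03 ng/ml appears once, 1.3 ng/ml three times, for the same analyte in the same unit, and no reason is given for the difference. Applied as written, 3.3.2.13 requires some women who count as non-luteal to be told of a result that needs no action, and permits a needless repeat draw.

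The effect stops there. Eligibility and scan timing rest on 1.3 ng/ml, the non-luteal phase or the pregnancy-test alternative, not on 0.03. No sample size, power, endpoint or analysis depends on the trigger. The conclusion assumes only that 3.3.2.13 is followed literally; how many women it would touch is unknown.

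**What to change.** Ask the sponsor to confirm that 1.3 ng/ml is the intended trigger, then replace 0.03 with 1.3 in the progesterone sentence of 3.3.2.13 so that it agrees with 3.3.2.5, 3.3.2.9 and 4.4.1. If 0.03 is deliberate, add a clause saying what it is for. Either way the cost is one figure or one clause in one sentence, with no consequence for the design or the analysis.

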2.2.g. Study 4 Streeter et, al 2017: Study 4 is a dosing study that filled a gap in the literature, as there were no published studies on the optimal dose of a hatha yoga intervention for MDD. Study 4 refined the Study 2 Iyengar yoga protocol by adding a 20-minute coherent breathing exercise at five breaths per minute to further increase PNS activation, thereby maximizing the effect of the intervention. This increased the intervention to 90-minutes, ~60-minutes of postures, transitions and 20-minutes of coherent breathing. The dosing study was a longitudinal RCT wherein subjects with MDD were randomized to 12 weeks in a high dose group (HDG) of three 90-minute yoga classes per week and four 30-minute homework sessions, or a low dose group (LDG) of two 90-minute yoga classes per week and three 30-minute homeworks. Eligible subjects, 18-64 years old with MDD, had baseline Beck Depression Inventory II (BDI-II) scores ≥ 14 (with higher scores representing greater depressive symptom severity) and were not on antidepressants, or were on a stable dose of antidepressants for ≥ 3 months. Exclusion criteria included current psychotherapy for depression, history of psychosis or bipolar disorder, active alcohol or substance abuse, history of suicidal ideation with intent within the last year (suicidal ideation without intent was allowed), current mind-body practices, nicotine use, more than 5 drinks on three occasions in the last 3 months, and medications directly affecting GABA receptors (e.g., sedatives benzodiazepines, antiseizure medications). Anxiety Disorders were allowable and resulted in the enrollment of the following: 8 PTSD current, 1 PTSD in full remission, 4 PTSD sub-threshold, 3 Panic Disorder in partial remission, 1 Panic Disorder in full remission, and 1 Social Phobia current.

2.2.h. Depressive Symptoms, Compliance and Safety (Figure 2): Retention was excellent, with 93% (30/32) of randomized subjects completing the study: HDG (n = 15), and LDG (n=15). Compliance was excellent for classes, homework and total yoga minutes. Compliance for total yoga minutes was $87 \pm 28\%$ for the HDG and $84 \pm 19\%$ for the LDG, with no difference in compliance between groups ($p = 0.77$). This resulted in a significant difference between groups in total yoga minutes with $4,075 \pm 1,314$ minutes for the HDG and $2,737 \pm 625$

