- (10) **Pittsburgh Sleep Quality Index (PSQI)** is a self-administered instrument that assesses 9 factors of sleep over a month period, providing a composite score, with higher scores indicating poorer sleep quality.(71)
- (11) **Timeline Follow Back (TLFB)** will be used to assess alcohol consumption for three months prior to screening.(72) A format similar to the TLFB will be used for nicotine consumption.
- (12) **Brief Pain Inventory**, an eleven point Likert Scale of pain intensity will be used to assess pain over the last 24 hours.
- (13) **Stroop Color-Word Test** is a selective attention and inhibitory cognitive control task.(74)

Individual Time Line	Table 3: Individual Time Line and Collection of Dependent Variables		
	Aim 1	Aim2	Aim 3
Individual Time Line	Depression Scales	Mood Scales	GABA RSA
Telephone Screen			
Screening Session	HDRS/BDI-II 1		
3T Brain Scan			
MRS Imaging Session 1			
Pre Scan 1 Measures	HDRS/BDI-II 2	EIFI & STAI 1	RSA 1
MRS Scan 1(Baseline)			GABA 1
Randomization			
Week 4			
Pre-Week 4 Evaluation		EIFI & STAI 2	RSA 2
Week 4 Intervention			
Post-Week 4 Evaluation	HDRS/BDI-II 3	EIFI & STAI 3	RSA 3
Week 5-7 Intervention			
Week 8			
Pre-Week 8 Evaluation		EIFI & STAI 4	RSA 4
Week 8 Intervention			
Post-Week 8 Evaluation	HDRS/BDI-II 4	EIFI & STAI 5	RSA 5
Week9-11 Intervention			
Week 12			
Pre-Week 12 Evaluation		EIFI & STAI 6	RSA 6
Week 12 Intervention			
Post-Week 12 Evaluation	HDRS/BDI-II 5	EIFI & STAI 7	RSA 7
MRS Imaging Session 2			
Pre Scan 2 Evaluation	HDRS/BDI-II 6	EIFI & STAI 8	RSA 8
Scan 2			GABA 2
Interscan Intervention			
Pre-Scan 3 Evaluation		EIFI & STAI 9	RSA 9
Scan 3			GABA 3
Follow-Up 2 month	HDRS/BDI-II 6	EIFI & STAI 10	
Follow-Up 6 month	HDRS/BDI-II 6	EIFI & STAI 11	

(14) **Digit Symbol Substitution Test (DSST)** is one of the frequently used tests to measure psychomotor slowing, and is clinically sensitive because it makes demands on several processes, including perception, working memory, sustained attention and visuomotor co-ordination (Wechsler 1997).

(15) **Child Trauma Questionnaire (CTQ)** is a self-report measure of childhood trauma. (73) This scale will be given during the Week 4 evaluation at the end of the session.

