Unless otherwise stated, instruments 4-12 are used at screening, week 4, 8, and 12. In addition, the EIFI and STAI-State are administered before and after interventions at weeks 4, 8, and 12 and before each scan. The CAPS is administered at screening and at week 12. The following instruments are given at Imaging Session 1 & 2: 2, 5, 13, and 14.

Recruitment Plan and Requirements (Table 4): Veterans will be recruited from the Bedford VA Medical Center (VABHCS) through posters, the internet, providing flyers to clinics, in meetings with staff, and recruitment at clinics affiliated with the VABHCS. Veterans who had a diagnosis of depression in the previous two years at the VABHCS will be identified via electronic health records. Targeted letters signed by the PI describing the study and inviting the Veterans to call or mail for more information will be mailed to Veterans. The mailing will include opt-in or opt-out card with postage and/or an opt-in or opt-out phone number. If a card or phone is not received within 10 days of the mailing, the identified Veterans will be called concerning their interest in the study. Data Access Request Tracker (DART) and VA Informatics and Computing Infrastructure (VINCI) will be used to identify potential subjects.

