Assessment of suicide risk is done using the Columbia Suicide Severity Rating Scale (CSSR-S). The development of suicidality with intent based on the CSSR assessment will result in study withdrawal such that the participant can receive additional conventional treatment. If a member of the research staff concludes that suicidality with intent is present they will develop a safety plan with the participant that can include support by friends or family, the inclusion of their medical treaters, being taken to the VABHCS Mental Health Clinic, where admission to an in patient unit can be arranged. If there is a safety concern after 3:30 when the Mental Health Clinic closes, participants will be referred to Urgent Care or the Lahey Clinic that provides after hours emergency services for the VABHCS. If the participant can be managed safely as an outpatient, arrangement will be made for follow-up treatment. It is noteworthy suicidality decrease in Phase 1 in civilians and no subject were withdrawn from the study for increased symptoms.

3.3.2.15. Potential Problems: Recruitment goals will be assessed every 6 months. If recruitment falls behind schedule, study staff will meet with the staff from the numerous clinic programs at the VABHCS to inform them of this research opportunity. If enrollment in the imaging component is behind due to nicotine use causing more than 10% of exclusions in a 6 month period, the inclusion criteria regarding smoking will be increased to include all subjects, regardless of abstinence.

3.3.2.16. Acquisition of Mood Scales and Psychological Tests: Participants will enter self-report mood and psychological scales onto paper forms. Investigator completed psychological mood and psychological scales will be entered into the REDCap database by research staff. The computers used for storage of mood scales and psychological tests will be VA computers.

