4.6.1.10. Risk of Depression: This is a treatment study with modalities that are not approved for the treatment of depression. There are alternatives to participation, such as pharmacotherapy, psychotherapy or electroconvulsive, and subjects will be informed of these other options and of their right to withdraw from the study to seek conventional treatment. Subjects are screened for risk of suicide during the screening interview with the Columbia Suicide Safety Rating (C-SSR), a widely used instrument to assess suicide risk. It is noted that the C-SSR does not provide a score stating that the assessment of suicide is a clinical decision. For this reason, other than the development of suicidal ideation with intent, the decision to withdraw a subject remains a clinical matter that is informed by the assessments built into the study. There are assessments by a psychiatrist or member of the research staff licensed to assess for suicide risk at screening, and at the weeks 4, 8, and 12 assessments using the C-SSR. Safety Data from Study 4 showed that out of 30 subjects, 9 out of 10 subjects that endorsed suicidal ideation without intent at screening no longer endorsed suicidal ideation without intent at the end of the study. No subject developed suicidal ideation with or without intent during the study. Suicidal ideation with intent with in a year of screening was exclusionary. In addition, the C-SSR evaluation were in agreement with reports of self harm on the Beck's Depression Inventory II (BDI-II), consistent with both clinical evaluation and self-report with regards to safety being accurate. In the proposed study, staff will check question 9 of the BDI-II regarding self-harm before the participant

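### Emergent suicidality with intent leads to an undefined study withdrawal, and neither document provides for outcome or research safety assessments afterwards

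*Protocol*

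**What the plan says.** Protocol 3.3.2.14 states that suicidality with intent "based on the CSSR assessment will result in study withdrawal such that the participant can receive additional conventional treatment". Protocol 4.6.1.10 repeats the rule and makes it the single exception to clinical discretion: "other than the development of suicidal ideation with intent, the decision to withdraw a subject remains a clinical matter". After the event, 3.3.2.14 sets out clinical care only: a safety plan, referral or admission, and arrangements for treatment.

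Detection is frequent. "Participants are screened weekly for suicidality by use of an Adverse Events sheet" (3.3.2.14), and staff also assess suicidality at weeks 4, 8 and 12. The depression scales are less frequent. In 3.3.2.1, "Table 3: Individual Time Line and Collection of Dependent Variables" puts HDRS and BDI-II during the intervention only after the week 4, 8 and 12 sessions, then before Scan 2 and at 2 and 6 months.

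For the analysis, Protocol 3.5.1 and SAP D.17 specify a mixed linear model on baseline and weeks 4, 8 and 12 that accepts unequal numbers of time points per participant. People who change antidepressants stay in the intent-to-treat analysis, with the change as a covariate.

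**The concern.** HDRS change is part of the primary dependent variable (Protocol 3.2). A rule that ends participation when a participant becomes suicidal with intent makes later scores missing because of deterioration in the condition being measured. Visits already observed stay in the mixed model. Its estimates are valid, however, only if the observed data account for the dropout, and the last observed HDRS may predate the worsening. The model would then extrapolate from a better score than the participant's true state. Neither document plans a sensitivity analysis for this.

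There is also a cost in safety knowledge. The event is detected and managed clinically, and the data monitoring committee reviews adverse events and retention (4.6.2.1). What the plan does not provide for is the later research course by arm, namely whether depression and suicidality resolved. The protocol itself lists reduction of suicidal ideation among the knowledge to be gained (section 4.6.3).

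**Working it through.** **Reading the rule.** The plan gives no figure to reproduce, so the first step is textual.

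- *Mandatory?* Finding intent takes clinical judgement. Once it is found, 3.3.2.14 and 4.6.1.10 leave no discretion about withdrawal.
- *Sessions only?* No definition separates stopping yoga or walking from stopping assessments. Elsewhere (4.2, 4.5.1.2, 4.6.1.4, 4.6.1.10) withdrawing means leaving the study.
- *Assessments afterwards?* None is provided for. The 2- and 6-month calls (3.2) are not said to include withdrawn participants, and not said to exclude them.
- *Does the stated purpose require assessments to stop?* No. Conventional treatment and outcome assessment can run together. By analogy only, people who change antidepressants stay in the analysis; that text concerns analysis, not data collection after a crisis.

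**Timing.** There are 12 weekly screens and 3 evaluation weeks, so 12 − 3 = 9 weeks have a suicidality screen but no HDRS.

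**Loss per affected participant.** The modelled post-baseline visits are weeks 4, 8 and 12 (3 in all). Table 3 adds pre-Scan 2, 2 months and 6 months (6 in all). For Imaging Session 2, the text under 3.3.2.1 differs from the table: "The following instruments are given at Imaging Session 1 & 2: 2, 5, 13, and 14". That list includes C-SSRS and BDI-II but not HDRS, whereas Table 3 shows both depression scales. The entries below are occasions lost, by detection week.

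| Detection week | Of 3, that week's evaluation done | Of 6, done | Of 3, not done | Of 6, not done |
|---|---|---|---|---|
| 1–3 | 3 | 6 | 3 | 6 |
| 4 | 2 | 5 | 3 | 6 |
| 5–7 | 2 | 5 | 2 | 5 |
| 8 | 1 | 4 | 2 | 5 |
| 9–11 | 1 | 4 | 1 | 4 |
| 12 | 0 | 3 | 1 | 4 |
| Sum over 12 weeks | 21 | 57 | 24 | 60 |

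Assuming equally likely detection weeks:

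- evaluation in the detection week done: 21/12 = 1.75 of 3, and 57/12 = 4.75 of 6;
- evaluation not done, because withdrawal comes at the week's first session: 24/12 = 2.0 of 3, and 60/12 = 5.0 of 6;
- week-12 score lost: 11 of 12 detection weeks in the first case, 12 of 12 in the second.

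**Frequency.** For the pilot (Study 4), 4.6.1.10 reports on 30 subjects: "No subject developed suicidal ideation with or without intent during the study". The one-sided 95% upper bound for 0/30 is 1 − 0.05^(1/30) = 0.095, or 9.5%. This is indicative and not a maximum:

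- the 30 were the completers (2.2.h: "Retention was excellent, with 93% (30/32) of randomized subjects completing the study");
- all were civilians in yoga arms, so they say nothing about walking or Veterans;
- the count covers any new ideation, which is broader than the intent trigger.

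As a stress case, suppose both non-completers had had the event: 2/32 = 6.3%, with a one-sided 95% Clopper-Pearson upper bound of 18.4%. The protocol's own account argues against this: "no subject were withdrawn from the study for increased symptoms" (3.3.2.14, on the civilian phase).

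**The case against.** The strongest reply is that the harm depends on a reading. Nothing forbids later assessments. The sentence ties withdrawal to access to treatment, so it could mean only the end of study treatment, and the consent pages, which might define withdrawal, were not available to this review. Some information would also survive. Worsening triggers an evaluation, and a change in severity goes on the adverse-event forms (4.6.1.10). Participants authorise use of their VA health records (4.5.2.1). The 2- and 6-month calls are not restricted to completers.

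The trigger is also rare, and people with intent or an attempt in the past year are excluded at entry. The plan's own figures imply 84 − 70 = 14 (3.5.2) to 100 − 70 = 30 (4.5.2.9) non-completers, and it describes no assessment after withdrawal for any of them, so this rule may account for none or only a handful. Finally, scores after a crisis mix in new treatment, and whether they belong in the primary comparison depends on the question asked. The protocol calls the trial an efficacy study (3.2), while Aim 1 speaks of effectiveness.

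Rarity, the unseen consent text and the assumption behind the per-participant averages all stand, and they limit the weight of the point. The rest does not remove it. Adverse-event forms and medical records are not HDRS scores. Staff who are told that a participant is withdrawn from the study have no instruction to keep assessing. The wider gap for other dropouts is real, but here the protocol itself imposes the loss. If the scores are collected, the analyst can choose how to treat them; if they are not, the choice is gone.

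**Conclusion.** The concern holds. As written, the rule ends study participation on a worsening of the condition under study and provides for no outcome or research safety data afterwards. Per affected participant, the average loss is 1.75 to 2.0 of the 3 modelled visits and 4.75 to 5.0 of the 6 scheduled occasions. These figures assume equally likely detection weeks and that withdrawal stops all assessments, including the follow-up calls. The number affected is probably small, and the size and sign of any bias in the HDRS comparison cannot be derived. The rule should be changed because the loss is selective and cheap to avoid. It does not by itself undermine the trial. Confidence is medium, mainly because the term is undefined and the consent text was not seen.

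**What to change.** In 3.3.2.14, replace study withdrawal with discontinuation of the assigned intervention, leaving the trigger and safety plan as they are. In 3.3.2.14 and 4.6.1.10, state that, unless the participant declines, the remaining HDRS, BDI-II and C-SSRS assessments, adverse-event follow-up and the 2- and 6-month calls continue when clinically appropriate, remotely if needed, and that the data enter the intent-to-treat analysis. Report these discontinuations by arm.

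The cost is a short protocol amendment and matching consent wording, with no new instrument or visit. Remote routes already exist: the 2- and 6-month contacts are calls (section 3.2) at which Table 3 schedules HDRS and BDI-II, and the suicidality and safety plan section lets staff complete the weekly adverse-event form by phone. The downside is that some participants will decline, and later scores will include the effect of new treatment.
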